4 OUTCOME MEASURES

Primary outcome measures:

The primary endpoints in sub-study 1: VISA-A at 3 and 6 months. Collected by independent evaluator via “Redcap”.

The primary endpoints in sub-study 2: VISA-A (total and pain subscales) 6 months after the 1st injection date in substudy 2. Collected by independent evaluator via “Redcap”.

The primary endpoints in sub-study 3: VISA-A score at 6 and 12 months from the day of surgery.

All patients are thoroughly instructed in visa-A score, on all visits, as it can be difficult to understand. However, it is important that they fill out the score at home directly in the assessment-

app: "Redcap" without interference of any involved investigators. Intention to treat is used so that patients who do not show up for primary outcome will have scores transferred from the last attendance.

Secondary outcome measures

Sub-study 1:

Lickert scale at 3, 6, 9 and 12 months: 11 point box scale from -5 to +5, where 0 is the status at **entry**, +5 is cured, and -5 is much worse.

VISA-A scores 1,2, 9 and 12 months, including VISA-A pain subscore during Function at all timepoints (1,2,3,6,9,12 months)

Assessment of the exercise therapy at 3 months: 11 point box scale from 0-10, where 0 is very uninspiring / boring training, and 10 is very inspiring and motivating training.

Thickness of the Achilles tendon measured by ultrasound scan, cross-sectionel image on the thickest of the tendon at 3, 6, 9 and 12 months. The thickness of the "healthy" tendon is also measured for comparison.

Ultrasound Scanning Doppler Activity assessed with Color Doppler at 3, 6, 9 and 12 months.

After 6, 9 and 12 months, it is also assessed how many percentage of previous activity level (from before the injury) they have recovered. The patient himself states this as a percentage.

Survival rate to the treatment is assessed by assessing all patients that are not satisfied with the treatment or can not comply to the training protocol.

Sub-study 2:

VISA-A score 1, 2, 3, 9 and 12 months

Thickness of the Achilles tendon measured by ultrasound scan, cross-sectional image on the thickest part of the tendon at 3,6,9,12 months. The thickness of the "healthy" tendon is also measured for comparison.

Ultrasound Scanning Doppler Activity assessed with Color Doppler at 3, 6, 9 and 12 months.

After 6, 9 and 12 months, it is also assessed how many percentage of previous activity level (from before the injury) they have recovered. The patient himself states this as a percentage.

Any complications are noted on an ongoing basis.

Sub-study 3:

VISA-A score 3 months post operatively.

Thickness of the Achilles tendon measured by ultrasound scan, cross-sectional image on the thickest part of the tendon at 3, 6 and 12 months.

Ultrasound Scanning Doppler Activity assessed with Color Doppler at 3, 6 and 12 months.

After 6 and 12 months, it is also assessed how many % of previous activity level (from before the injury) they have recovered. The patient himself states this as a percentage.

Any complications are noted on an ongoing basis.

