In cases where the above treatment measures are ineffective, surgery may be considered. Surgery of midsection AT has been tried for many years. Traditionally with longitudinal incisions of the tendon in the thickened part, but in recent years mainly as a minor intervention with a removal of the peritendium around the tendon (tenolysis) – especially on the front of the tendon, where vascular ingrowth with nerve fibers is assumed to be a large part of the cause of the pain from the tendon. Ruergård A et al (2019) have indicated a success rate of 89% with painlessness and return to sports at the same level as before the Achilles problems. In addition to this study, there are only small retrospective series of the effect of tenolysis, and in all the studies it is unclear to what extent and how effectively conservative treatment has been tried.

The purpose of our study is to compare an app based daily home training with physiotherapist supervised slow heavy strength training combined with load reduction by abstaining from running and jumping activities. This will be interesting because app based training is less costly than physiotherapeutic guided training. In addition, we will compare 50 ml of HVI with CS with 2 ml of CS injection as a supplement to training, in those patients who do not achieve satisfactory results with training alone. Finally, patients with continued problems will be offered surgery with Achilles tenolysis in an open prospective study.

The study is based on the following hypotheses:

- 1) Treatment with an app based daily home workout is as effective as slow heavy strength training (non-inferiority study).
- 2) 50 ml HVI with CS is better than 2 ml CS injection in addition to continued training, in those patients who do not achieve satisfactory results with training alone (superiority study).

- 3) Surgery with surgical tenolysis results in a clinically relevant reduction of pain symptoms in patients without sufficient effect of structured and monitored conservative treatment (the above conservative regimen).

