5 SAMPLE SIZE AND POWER

Sub-study 1

The risk of finding a difference between groups, even if there really is none, is set at 5% (risk of type I error), while the risk of overlooking a difference between the groups that is actually present is set at 20% (type II error). All outcome parameters will be analyzed using Mixed Effect Analysis

Statistical Analysis Plan	Date: nov 27, 2022
Exercise/Injections/operation in Achilles midsubstance tendinopathy	
Bispebjerg Hospital	

with treatment regime (group) and time as main factor (GraphPad Prism version 9.3 for Windows, GraphPad Software, La Jolla California USA, www.graphpad.com). All analysis are performed as an intention-to-treat analysis. If a patient drops out due to no improvement or too much pain to continue exercise therapy, the missing data will still be included using the mixed effect analysis.

Q-Q plots will be visually examined prior to analysis to ensure that the assumption of normal distribution is not violated. Significance level is set to 0.05. We will also compare the “survival rate” in each training group, and compare the end result after training by performing per protocol analysis. Patients not complying at least 75% with the training protocol are not included in the per-protocol statistics.

The minimum relevant difference in VISA-A is set at 15. However, as a non-inferiority study, the difference is set to $15/2 = 7.5$. Based on other studies on pain intensity, we expect a mean baseline of 50 and an average improvement of 17. The standard deviation (SD) on the VISA-A measurements in these studies is 13. Power of 80% gives a sample size of 38 participants in each group. We plan to include 45 in each group in case of data loss and no-shows, for a total of 90 patients.

Sub-study 2:

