7.2 Statistical Analysis Plan

Statistical analysis will be undertaken using PRISM version 9.3.1. All analyses will be conducted on an intention-to-treat principle using all randomized participants in the groups they were originally randomized to. A blinded statistician will perform the data analysis. In the per-protocol analysis only patients complying at least 75% with the treatment protocol are included in the statistics.

A blinded statistician will perform the data analysis.

Demographic and anthropometric characteristics (gender, age, mass, height, body mass index, sporting activities and pain duration) will be determined at the baseline visit for each treatment group.

Statistical analyses will be conducted on all outcome measures at all timepoints. However, the primary end-point will be the total score of the VISA-A questionnaire at 3 and 6 months in substudy 1; VISA-A total score and pain-subscales at 6 months in substudy 2; and VISA-A total score at 6 and 12 months in substudy 3. Between-group comparisons of treatment effect for all primary and secondary outcomes, will be performed with a mixed effect analysis. To assess for inferiority and superiority, mean between-group differences and two-sided 95% confidence intervals will be calculated.

The ordinal scaled data of patients overall assessment of the treatment effect (Lickert score -5 to +5) will be analyzed with the same mixed effect analysis, if the data is found normally distributed.

The ordinal scaled data on satisfaction with the exercise program is analyzed with the same mixed effect analysis, if the data is found normally distributed.

The ordinal scaled data of grading the flow within the tendon into 4 categories will be calculated using non parametric statistics: Mann-Whitney U-tests.

Return to sport in percent of earlier sports activity will be compared using unpaired t-test if the data is normally distributed, otherwise non parametric analysis (Mann-Whitney) is performed.

In substudy 1 the survival rate in each exercise group is illustrated on a Kaplan-Meier plot and differences are calculated using Log rank test (Mantel-Cox test).

A two-sided P value of less than 0.05 will be considered to indicate statistical significance.

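### Sub-study 1 makes VISA-A at 3 and at 6 months both primary for one non-inferiority hypothesis, without a rule for combining them, and 38 per group covers only one comparison

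*SAP*

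**What the plan says.** Hypothesis 1 in SAP section 1 is one claim: app-based training is non-inferior to heavy slow resistance training. Two time points are attached to it. Section 4 says "The primary endpoints in sub-study 1: VISA-A at 3 and 6 months", and section 7.2 says "the primary end-point will be the total score of the VISA-A questionnaire at 3 and 6 months in substudy 1".

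Section 5 sets the non-inferiority margin at 7.5 VISA-A points, half of a minimum relevant difference of 15. It adds "The standard deviation (SD) on the VISA-A measurements in these studies is 13" and "Significance level is set to 0.05", sets the type II error at 20%, and concludes "Power of 80% gives a sample size of 38 participants in each group". Recruitment is set at 45 per group to allow for data loss and no-shows. The calculation names no time point and does not say whether the 5% is one-sided or two-sided.

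Section 7.2 plans between-group differences from a mixed effect analysis with two-sided 95% confidence intervals, and two-sided significance at 0.05. No section says how the month 3 and month 6 results together decide hypothesis 1.

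**The concern.** With two primary results and one hypothesis, the success criterion depends on a rule that the SAP does not state. If either month is enough, there are two chances to declare non-inferiority falsely. If both are needed, the error rate is protected but the trial can fail at either month, and a sample size for one comparison is too small. If the months disagree, hypothesis 1 has no defined answer and the rule would be chosen with the results in view.

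Disagreement is plausible. Month 3 closes the controlled training period, and a gradual return to sport follows (section 3). Patients may leave for sub-study 2 after one month of training, and section 5 expects about 67 of the 90 to want additional treatment and 50 to continue there. The SAP does not say when these moves occur, but they accumulate, so month 6 has at least as many as month 3.

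**Working it through.** **Inputs from SAP section 5:** margin 7.5, SD 13, power 80%, type I error 5%, 38 per group needed, 45 per group recruited. **Input from section 7.2:** two-sided 95% intervals, that is, one-sided 2.5% against the margin. **Assumptions, not in the SAP:** true difference 0 at both months, SD 13 at both months, normal approximation, and correlation r = 0.5 between the month 3 and month 6 estimated differences (range 0.3 to 0.7).

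**Step 1: reproduce the 38.** For one comparison, n per group = 2 × SD² × (z for alpha + z for power)² / margin².
- One-sided 5%: 2 × 169 × (1.645 + 0.842)² / 56.25 = 37.2, so 38. A t-based calculation also gives 38.
- One-sided 2.5%: 2 × 169 × (1.960 + 0.842)² / 56.25 = 47.2, so 48 (49 with t). This does not give 38.

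The stated figure is therefore one comparison at one-sided 5%.

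**Step 2: power at one month.** SE = 13 × √(2/n), and power = Φ(7.5/SE − z).
- n = 38: SE = 2.98 and 7.5/SE = 2.515. Power is Φ(2.515 − 1.645) = 81% at one-sided 5% and Φ(2.515 − 1.960) = 71% at one-sided 2.5%.
- n = 45: SE = 2.74 and 7.5/SE = 2.737. Power is 86% and 78% respectively.

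**Step 3: two months.** Let Φ₂(a, a; r) be the probability that two standard normal variables with correlation r both lie below a.
- Both required: power = Φ₂(7.5/SE − z, 7.5/SE − z; r).
- Either sufficient: false non-inferiority, with the true difference on the margin at both months, = 1 − Φ₂(z, z; r). This does not depend on n.

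| Basis | One month: power | Both required: power, r = 0.5 (0.7 to 0.3) | One month: error | Either sufficient: error, r = 0.5 (0.7 to 0.3) |
|---|---|---|---|---|
| One-sided 5%, n = 38 | 81% | 70% (72 to 68%) | 5% | 8.8% (8.0 to 9.3%) |
| One-sided 5%, n = 45 | 86% | 78% (80 to 76%) | 5% | 8.8% (8.0 to 9.3%) |
| One-sided 2.5%, n = 38 | 71% | 57% (60 to 54%) | 2.5% | 4.5% (4.2 to 4.8%) |
| One-sided 2.5%, n = 45 | 78% | 66% (69 to 64%) | 2.5% | 4.5% (4.2 to 4.8%) |

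**Step 4: sensitivity to r at one-sided 5%.** At r = 0, power with both required at n = 38 is 65%, and the error with either sufficient is 9.75%. At r = 0.9 the figures are 76% and 6.8%.

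**Step 5: evaluable patients per group for 80% power if both are required.** At one-sided 5%: 51, 48 and 46 for r = 0, 0.5 and 0.7. At one-sided 2.5%: 62, 59 and 57.

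**Step 6: power of an either rule with the section 7.2 intervals at n = 38.** This is 2 × one-month power − both power. At r = 0.3 it is 2 × 0.710 − 0.542 = 88%, and at r = 0.7 it is 2 × 0.710 − 0.603 = 82%.

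**The case against.** A reader might infer that whichever rule is used, either the stated 5% error or the stated 80% power must fail. The SAP does not support that. With the two-sided 95% intervals of section 7.2, an either rule and 38 evaluable per group, false non-inferiority is 4.2 to 4.8% and power is 82 to 88%, so both stated figures are met. The strict either/or holds only on the one-sided 5% basis that yields 38. What remains is that 4.5% exceeds the 2.5% implied by the interval, and that the SAP does not adopt this rule.

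A reader might also infer that the plan has no non-inferiority criterion at all. That goes too far. The margin is in section 5 and the interval in section 7.2, although they are never explicitly joined. The clear gap is the rule for combining the months. Naming the two months together can naturally be read as requiring both. The error is then protected and only the power is affected.

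The shortfall under the two-sided intervals should not be blamed wholly on the two months. The fall from 81% to 71% at 38 per group comes from deriving the size at one-sided 5% and analysing at one-sided 2.5%, which is a separate problem. The further fall to 57% comes from requiring both.

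Finally, the 45 per group soften the result: if all were evaluable at one-sided 5%, requiring both would give 76 to 80%. Section 5 holds the extra 7 per group for losses, so this cannot be counted on.

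**Conclusion.** The point stands as a missing combination rule with a sample size that covers one comparison. On the basis that produces 38 per group, requiring both months lowers power by about 11 percentage points to 70%, and accepting either raises the false non-inferiority rate from 5% to 8.8%. Only one of these can apply under a given rule: requiring both cannot inflate the error, and accepting either cannot reduce the power.

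With the planned two-sided 95% intervals, requiring both gives 57% with 38 evaluable per group, or 66% if all 45 are evaluable.

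The sizes rest on the assumed correlation and a true difference of 0. Neither is in the SAP, but the direction holds at every correlation checked from 0 to 0.9. The absence of the rule needs no assumption. It matters because it leaves the success criterion of sub-study 1 open.

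**What to change.** Amend sections 4 and 7.2 before unblinding, in one of two ways.

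1. Name one primary month and test the other only if the first shows non-inferiority. The fixed order keeps the error at its nominal level without splitting alpha. Month 3 is a reasonable choice, since it ends the training programme and can have no more transfers to sub-study 2 than month 6. The SAP does not rank the months, however, and the choice is the sponsor's.
2. State that both months must clear the 7.5 margin, and restate the power in section 5 for the evaluable number per group at the confidence level actually used. Quoting power for all 45 would ignore the allowance for losses.

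Either way, say which confidence limit is compared with 7.5 and at what level.

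The cost is SAP wording. Section 7.4 reports that no analysis had begun at signing, and section 5 places the analysis after the last patient's 12-month follow-up. The downside is that one month loses its co-primary status, or that the stated power becomes less favourable.

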In a previous study, 25% achieved satisfactory effect from training alone. If the same is seen in the current study, approximately 67 will want additional treatment. Of these, we expect that 50 will continue in sub-study 2. Sub-study 2 is a superiority study, and 22 patients are needed to have an 80% chance of finding, with 5% significance level, a difference in VISA-A scores of more than 11 between treatment groups using Mixed Effect Analysis using the intention to treat principle. Patients are divided into 4 groups, but this sub study will be powered to detect differences between exercise therapy+HVI and Exercise therapy +CS injection. This means that the combination of group 3 and group 5 are compared to the combination of group 4 and group 6. However, we will also compare group 3 to group 4, and group 5 to group 6.

Q-Q plots will be visually examined to ensure that the assumption of normal distribution is not violated prior to analysis.

Sub-study 3

	Statistical Analysis Plan	Date: nov 27, 2022
Bispebjerg Hospital	Exercise/Injections/operation in Achilles midsubstance tendinopathy	

is a prospective quality assurance study. Paired T-test is used for calculating differences from before operation to 3, 6 and 12 months after operation. Change in VISA-A score is the primary outcome at 6 and 12 months, with an expected preoperative score of 50 and a relevant improvement is set to 15. The standard deviation of the difference is from earlier studies 13. In order to record an improvement of at least 15 points with a risk of type I error of 5% and type II error of 20%, 8 patients would have to be included in this study.

Data processing:

Entry data is registered in Redcap, where all information from each individual subject is collected.

Each patient is assigned an anonymous unidentifiable project number: Ach2019-n.

Project numbers are listed on all CRF and patient diaries.

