7.4 Timing of analyses

When this statistical analysis plan was signed, recruitment to the main trial was started, but no analysis had been initiated.

SUB-STUDY 1								
	Enrolment	Allocation						
TIMEPOINT	april 2022 – end 2024	april 2022 – end 2024	Month 1	Month 2	Month 3	Month 6	Month 9 Jan 2023 end 2025	Month 12 April 2023 end 2025
ENROLMENT:								
Eligibility screen	X	X						
Informed consent		X						
Allocation		X						
INTERVENTIONS:								
Intervention group 1			←————→					
Intervention group 2			←————→					
ASSESSMENTS:								
Diagnosis		X						
VISA-A		X	X	X	X	X	X	X
Morning pain [VAS]		X	X	X	X	X	X	X
Pain after activity [VAS]		X	X	X	X	X	X	X
Return to usual sports participation						X	X	X
Satisfaction with result of treatment			X	X	X	X	X	X
Patient diary for reporting compliance and adverse events			←————→					
Ultrasound examinations		X	x	x	X	X	X	X
Demographics		X						

Table 1: SPIRIT figure. Schedule of enrolment, interventions and assessments

SUB-STUDY 2								
	Enrolment	Allocation						
TIMEPOINT	July 2022 – July 2024	July 2022 – July 2024	Month 1	Month 2	Month 3	Month 6	Month 9 Jan 2023 end 2025	Month 12 April 2023 end 2025
ENROLMENT:								
Eligibility screen	X	X						
Informed consent		X						
Allocation		X						
INTERVENTIONS:								
Exercise group 3+4			←————→					
Exercise group 5+6			←————→					
ASSESSMENTS:								
Diagnosis		X						
VISA-A		X	X	X	X	X	X	X
Morning pain [VAS]		X	X	X	X	X	X	X
Pain after activity [VAS]		X	X	X	X	X	X	X
Return to usual sports participation						X	X	X
Satisfaction with result of treatment			X	X	X	X	X	X
Patient diary for reporting compliance and adverse events			←————→					
Ultrasound examinations		X	x	x	X	X	X	X
Demographics		X						

SUB-STUDY 3					
	Enrolment	Allocation			
TIMEPOINT	End 2022 – end 2025	End 2022 – end 2025	Month 3	Month 6	Month 12 End 2023 – end 2026
ENROLMENT:					
Eligibility screen	X	X			
Informed consent		X			
Allocation		X			
INTERVENTIONS:					
operation		x			
ASSESSMENTS:					
Diagnosis		X			
VISA-A		X	X	X	X
Morning pain [VAS]		X	X	X	X
Pain after activity [VAS]		X	X	X	X
Return to usual sports participation				X	X
Satisfaction with result of treatment			X	X	X
Patient diary for reporting compliance and adverse events					
Ultrasound examinations		X	X	X	X
Demographics		X			

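### Sub-study 2 lists VISA-A total and pain subscales as unranked primary endpoints, each judged at 0.05 with no decision rule, but is sized for one test

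*SAP*

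**What the plan says.** Section 4 of the SAP gives, for the injection comparison: "The primary endpoints in sub-study 2: VISA-A (total and pain subscales) 6 months after the 1st injection date in substudy 2". Section 7.2 restates the primary endpoint as "VISA-A total score and pain-subscales at 6 months in substudy 2". Both places put the total and the subscales on one line, with neither ranked above the other. Neither says which pain subscales are meant or how many there are.

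Section 7.2 sets one threshold for everything: "A two-sided P value of less than 0.05 will be considered to indicate statistical significance".

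Section 5 sizes sub-study 2 on one comparison: "22 patients are needed to have an 80% chance of finding, with 5% significance level, a difference in VISA-A scores of more than 11". The contrast is fixed: "this sub study will be powered to detect differences between exercise therapy+HVI and Exercise therapy +CS injection", meaning groups 3 and 5 pooled against groups 4 and 6 pooled. On recruitment it says: "Of these, we expect that 50 will continue in sub-study 2". It gives no difference or standard deviation for a pain subscale.

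The hypothesis at stake is the second one in section 1, that "50 ml HVI with CS is better than 2 ml CS injection in addition to continued training", described there as a superiority question.

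**The concern.** With several primary endpoints, a plan has to say what counts as success. Success could mean any one endpoint, all of them, or a fixed order, and each choice has its own error rate and power. This SAP names the primaries and the threshold but not the rule.

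If a pain subscale reaches significance and the total does not, or the reverse, the plan supports either answer to hypothesis 2. The choice could then be made after the results are known. Under an any-one reading the false-positive rate exceeds the 5% on which section 5 rests. Under an all-required reading the power is below the stated 80% at the stated sample size.

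**Working it through.** **Inputs from the SAP.** Difference 11, significance 5%, power 80%, 22 patients and 50 expected (section 5, sub-study 2); two-sided testing (section 7.2).

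**Assumptions.**
- SD 13, which section 5 gives for sub-study 1 and not for sub-study 2.
- Two or three primary endpoints (the total plus one or two subscales).
- Equal correlation of 0.7 to 0.9 between the test statistics.
- The same standardised effect on every endpoint, for the power figures.

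All calculations use the normal approximation.

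**Step 1: reproduce the sample size.**

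n per arm = 2 × ((1.96 + 0.842) × 13 / 11)² = 21.9, so 22 per pooled arm.

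The expected standardised difference at 22 per arm is d = 11 / (13 × √(2/22)) = 2.81, and the power is Φ(2.81 − 1.96) = 80.1%. A t-based calculation gives 23 per arm. Read as 22 in total (11 per arm), power is only 51%. The 22 is therefore taken as per pooled arm, for a single two-sided 5% test.

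The 50 expected patients give 25 per pooled arm. There d = 11 / (13 × √(2/25)) = 2.99, and single-test power is Φ(2.99 − 1.96) = 85%.

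**Step 2: error if any one success counts.** With no true effect on any endpoint:

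- two-sided error = 1 − P(every |Z| ≤ 1.96)
- error in favour of HVI = 1 − P(every Z ≤ 1.96)

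| Correlation | Two endpoints, two-sided | Three endpoints, two-sided | Two endpoints, HVI only | Three endpoints, HVI only |
|---|---|---|---|---|
| 0.9 | 7.0% | 8.4% | 3.5% | 4.2% |
| 0.8 | 7.8% | 9.8% | 3.9% | 4.9% |
| 0.7 | 8.3% | 10.9% | 4.2% | 5.5% |

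A single test gives 5% two-sided and 2.5% in favour of HVI. Lower correlation makes it worse. At 0.5 the two-sided error is 9.1% with two endpoints and 12.5% with three. With independent tests it is 1 − 0.95² = 9.75% and 1 − 0.95³ = 14.3%.

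**Step 3: power if all must succeed.** Power = P(every Z + d > 1.96), with d from step 1.

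| Correlation | Two endpoints, 22 per arm | Two endpoints, 25 per arm | Three endpoints, 22 per arm | Three endpoints, 25 per arm |
|---|---|---|---|---|
| 0.9 | 75.2% | 80.7% | 72.3% | 78.3% |
| 0.8 | 73.1% | 79.0% | 68.8% | 75.3% |
| 0.7 | 71.5% | 77.7% | 66.1% | 73.0% |

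To reach 80% with all required takes 25, 26 or 27 per arm for two endpoints (correlation 0.9, 0.8, 0.7), and 26, 28 or 29 for three.

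**Step 4: power if alpha is split.** With 0.025 on each of two endpoints the critical value is 2.24. Power on the total is Φ(2.81 − 2.24), about 71%, at 22 per arm and Φ(2.99 − 2.24), about 77%, at 25. Reaching 80% takes 27 per arm, or 54 patients, against 50 expected.

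Section 5 also plans to compare group 3 with group 4 and group 5 with group 6. Those tests are not counted in any figure above.

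**The case against.** The milder reading is that VISA-A is one instrument, with the total as anchor and the pain items as components reported beside it. Section 5 supports this in part, because it sizes VISA-A scores on one pooled contrast. But sections 4 and 7.2 both give the subscales the same primary status as the total, and nothing says the total decides.

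The definition of the subscales may well stand in the protocol, so their absence from the SAP carries little weight. Section 4 does mention a VISA-A pain subscore during function, but as a sub-study 1 secondary outcome, which does not settle what the plural means in sub-study 2. The missing decision rule is the substance of the point.

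The size is conditional. The SAP gives no endpoint count, no correlation and no SD for sub-study 2, so only the direction is certain. With two endpoints the effect is modest: 3.5% to 4.2% against 2.5% for a false claim in favour of HVI, and all-required power of 78% to 81% at 25 per arm. That last figure assumes all 50 expected patients provide data. This objection stands, and it limits how serious the point is.

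There are also safeguards. The timepoint and the powered contrast are fixed, section 7.2 promises mean differences with 95% confidence intervals, and the data-processing text in section 5 has the results agreed before the blind is broken. These narrow the room for selective reporting. They do not settle which endpoint carries the claim, because blinding to group does not hide which endpoint is significant.

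**Conclusion.** The concern holds. Sub-study 2 has at least two unranked primary endpoints, one unadjusted two-sided 0.05 threshold, and a sample size consistent with a single test. Read one way, the plan exceeds its 5% error. Read the other way, it falls short of its 80% power at the 22 per arm it calculates. At the 25 per arm it expects, all-required power is close to 80% for two endpoints and below it for three.

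The direction does not depend on the assumed values, short of perfectly correlated endpoints. The exact figures do depend on the assumed number of endpoints and correlation and, for power, on the SD and the equal standardised effect; they should be read as illustrative. This should be corrected, but it does not undermine the design.

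**What to change.** Before unblinding, amend sections 4 and 7.2 so that VISA-A total at 6 months, pooled HVI versus pooled CS, is the single primary endpoint of sub-study 2. Name the pain subscale or subscales, and test them only if the total is significant; otherwise report them as secondary. This stays consistent with the section 5 calculation: 80% power at 22 per arm and 85% at 25, under SD 13.

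Two other rules would also close the gap. One is to state that all primaries must succeed and restate the power as in step 3. The other is to split alpha and restate the power as in step 4. Both cost power, and stating some rule matters more than which one is chosen.

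The cost is SAP text. If the protocol lists the same primaries, the change also needs an entry in the section 8 deviation table and alignment of the protocol. Section 7.4 says that "recruitment to the main trial was started, but no analysis had been initiated" when the SAP was signed, so the SAP records no analysis that would stand in the way. The downside of the preferred rule is that a pain subscale cannot support a confirmatory claim if the total fails.
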